2.4.5.1 Analyses of hypoglycemia

Analyses of hypoglycemia will be performed on the TEAE period as defined in [Section 2.1.4](#). Hypoglycemia will be classified as severe hypoglycemia, documented symptomatic hypoglycemia, asymptomatic hypoglycemia, probable symptomatic hypoglycemia or relative hypoglycemia (see [Section 2.1.4.1](#)).

The number (%) of patients with any hypoglycemia, severe hypoglycemia and documented symptomatic hypoglycemia will be summarized respectively by treatment group during the TEAE period, as well as the incidence rate in patient years. Two types of incidence rates will be presented: the number of patients with at least 1 event per 100 patient-years (calculated as the number of patients with at least 1 event / total exposure in 100 patient-years), and the number of events per 100 patient-years (calculated as the total number of events / total exposure in 100 patient-years). Note: here exposure (in days) is the duration of TEAE period, ie, duration of IMP treatment in days +1 (see [Section 2.1.4](#)).

Statistical Analysis Plan

Version: 3

Lexicon Pharmaceuticals Protocol No. EFC14833

Date of Issue: 21-Nov-2019

Covance Study ID: 000000150524

The summary of frequency and incidence rate in patient years for severe hypoglycemia or documented symptomatic hypoglycemia will be provided as appropriate by gender (Male, Female), age group (<50, \geq 50 to <65, \geq 65 years), race (White, Black or African American, Asian, Other).

A KM curve will also be provided by treatment group for the time to first severe hypoglycemia or documented symptomatic hypoglycemia during the TEAE period (see [Section 2.5.4](#)).

Documented symptomatic hypoglycemia maybe presented by \leq 3.9 mmol/L (\leq 70 mg/dL) and $<$ 3.0 mmol/L ($<$ 54 mg/dL) respectively, as appropriate.

A listing of patients for all events reported on the dedicated e-CRF “Hypoglycemic event information” page will be provided with each category flagged (ie, severe hypoglycemia, documented symptomatic hypoglycemia, asymptomatic hypoglycemia, probable symptomatic hypoglycemia and relative hypoglycemia).

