- There is no intercurrent disease, which may jeopardize glycemic control (eg, infectious disease)
- Compliance to treatment is appropriate
- Compliance to diet and lifestyle is appropriate
- Assess plasma glucose in fasting condition (ie, after at least 8 hours fast)
- Initiate an evaluation and treatment of intercurrent disease (to be reported in AE/concomitant medication parts of the e-CRF and the medical record)
- Stress the absolute need to be compliant with treatment
- Organize a specific interview with the patient and a Registered Dietician or other qualified nutrition professional to reinforce the absolute need to be compliant with diet and lifestyle recommendations, and schedule a FPG assessment at the next visit.

In the event that a confirmatory FPG exceeds the threshold, the Investigator should ensure that no reasonable explanation exists for insufficient glucose control and in particular that:

If any of the above can reasonably explain the insufficient glycemic control, the Investigator should consider not initiating rescue medication and should undertake appropriate action, ie:

If none of the above mentioned reasons can be found, or if appropriate action fails to decrease FPG under the threshold values, rescue medication may be introduced.

Initiation of open-label rescue medication(s) to treat hyperglycemia will be at the discretion of the Investigator and in accordance with local standard of care and prescribing practice; except for SGLT2 inhibitors, any approved medication(s) including oral antidiabetic drugs or insulin can be prescribed to treat the hyperglycemia. The patient continues the study treatment (blinded) and stays in the study in order to collect efficacy and safety information. The planned visits and assessments should occur until the last scheduled visit. For patients with renal impairment, contraindications to antihyperglycemic drugs should be taken into consideration. If a patient requires glycemic rescue, the IMP received during the randomized, double-blind Treatment Period should continue and must remain blinded until the end of the study.

Rescue therapy is considered a noninvestigational medicinal product (NIMP). Rescue therapy is to be reported in the e-CRF. This information should include specific drug name, dose, route of administration, and frequency.

If not covered by health insurance, the cost of the rescue therapy will be reimbursed by the Sponsor where permitted by local regulations.

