## **Observation period of safety endpoints**

The observation period of safety data will be divided into 3 segments:

- The pre-treatment period is defined as the time between the date of the informed consent and the first dose of double-blind IMP.
- The on-treatment period (TEAE period) is defined as the time from the first dose of double-blind IMP up to 10 days (1 day for hypoglycemia) after the last dose of double-blind IMP, regardless of the introduction of rescue therapy. The 10-day interval is chosen based on the half-life of the IMP (approximately 5 times the half-life of sotagliflozin) in patients with moderate renal dysfunction.
- The post-treatment period is defined as the time starting 11 days after the last dose of double-blind IMP (after the on-treatment period).

The baseline value for safety endpoints in the safety population is the last available value (or the average of all values for creatinine or eGFR) prior to the first administration of the double-blind IMP.

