#### **10.4.2 General guidelines for reporting adverse events**

- All AEs, regardless of seriousness or relationship to IMP/NIMP, spanning from the signature of the ICF until the end of the study as defined by the protocol for that patient, are to be recorded on the corresponding page(s) or screen(s) of the e-CRF.
- Whenever possible, diagnosis or single syndrome should be reported instead of symptoms. The Investigator should specify the date of onset, intensity, action taken with respect to IMP, corrective treatment/therapy given, additional investigations performed, outcome, and his/her opinion as to whether there is a reasonable possibility that the AE was caused by the IMP or by the study procedure(s).

- In this study, the use of concomitant medications including antidiabetic medications may make it difficult to assess the causal relationship, particularly for hypoglycemia. Global Safety Officer with input from other appropriate study team members will determine the causal relationship when it is not clearly provided by the Investigator.
- The Investigator should take appropriate measures to follow all AEs until clinical recovery is complete and laboratory results have returned to normal, or until progression has been stabilized, or until death, in order to ensure the safety of the patients. This may imply that observations will continue beyond the last planned visit per protocol, and that additional investigations may be requested by the monitoring team up to as noticed by the Sponsor.
- When treatment is prematurely discontinued, the patient's observations will continue until the end of the study as defined by the protocol for that patient.
- Laboratory, vital signs or ECG abnormalities are to be recorded as AEs if they are medically relevant based on the investigator's medical judgment, eg,:
  - Symptomatic and/or
  - Requiring either corrective treatment or consultation, and/or
  - Leading to IMP discontinuation or modification of dosing, and/or
  - Fulfilling a seriousness criterion, and/or
  - Defined as an AESI or EOSI

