2.1.2 Prior or concomitant medications

All medications taken within 3 months before the screening visit (any time for prior SGLT2) and until the end of the study are to be reported in the electronic case report form (e-CRF).

All medications will be coded using the World Health Organization-Drug Dictionary (WHO-DD) using the version currently in effect at Covance at the time of database lock.

- Prior medications are those the patient used prior to first administration of double-blind IMP. Prior medications can be discontinued before first administration or can be ongoing during treatment phase.
- Concomitant medications are any treatments received by the patient concomitantly to the IMP, from the 1st administration of double-blind IMP to the date of last administration + 10 days. A given medication can be classified both as a prior medication and as a concomitant medication.
- Posttreatment medications are those the patient took in the period running from the 11th day after the last administration of double-blind IMP up to the end of the study.

Any technical details related to computation, dates, imputation for missing dates are described in [Section 2.5](#).

2.1.2.1 *Rescue therapy*

Except for SGLT2 inhibitors, any approved medication(s) including oral antidiabetic drugs or insulin can be prescribed to treat the hyperglycemia at the discretion of the investigator. Rescue therapy is considered a noninvestigational medicinal product (NIMP).

2.1.2.2 *Prohibited prior and concomitant medications*

During the study treatment period, the following medications are prohibited:

- Initiation of any antidiabetic agents, including oral or injectable antihyperglycemic agents other than the IMP is not allowed before the rescue therapy
- Systemic use of glucocorticoids is not allowed for more than 10 consecutive days (topical, ophthalmic, nasal spray or inhaled applications are allowed)
- Initiation of any weight loss drugs (eg, phentermine, orlistat)
- Investigational medicinal products in any other clinical study
- SGLT2 inhibitors (eg, canagliflozin, dapagliflozin, or empagliflozin) are not allowed for rescue.

Note: short term use (<10 consecutive days) of the prohibited medication, eg, short-acting insulin for treatment of acute illness or surgery is allowed.

Reduction of digoxin dose should be considered because sotagliflozin acts as a weak P-gp inhibitor and increases systemic exposure to digoxin.

Statistical Analysis Plan

Version: 3

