- The **screening** epoch is defined as the time from the signed informed consent date up to the first administration of the double-blind IMP.
- The **treatment** epoch is defined as the time from the first administration of the double-blind IMP to the last administration of the double-blind IMP.
- The **residual treatment** epoch is defined as the time from the last administration of the double-blind IMP up to 10 days (1 day for hypoglycemia) after the last administration of the double-blind IMP.

The treatment-emergent adverse event (TEAE) period will include both **treatment** and **residual treatment** epochs.

- The **posttreatment** epoch is defined as the period of time starting the day after the end of the treatment-emergent adverse event period up to the last protocol-planned visit or the resolution/stabilization of all serious adverse events (SAE), adverse events of special interest (AESI) and events of special interest (EOSI), whichever is later.

The on-study observation period is defined as the time from start of double-blind treatment until the end of the study (defined as the last scheduled visit for those who completed the study and the date collected on e-CRF page “Completion of End of Study/Follow-up” for those who did not complete the study).

The post-study observation period is defined as the time from the day after the end of the study until the resolution/stabilization of all SAE, AESI and EOSI if applicable.

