As specified in the study protocol, laboratory data from scheduled visits are reported by central laboratories. The local results will not be used in the efficacy analyses or in the definition of baseline for both safety and efficacy analyses. In the safety analyses, for parameters with PCSA defined based on normal range, local results will only be used in the PCSA summary if they are accompanied by a local laboratory normal range. For parameters with PCSA not defined based on normal range, local results will be used in the PCSA summary as appropriate.

When a patient has more than 1 measurement from the central laboratory for the same laboratory parameter on the same date, the average of the measurements will be used. For the same laboratory parameter, if a patient has more than 1 measurement on different dates for the same scheduled visit, the value closest to the date of the visit will be used for the scheduled visit. When the values for the same scheduled visit are equidistant, the last value should be used for the scheduled visit. Similar rules will be applicable to a patient who has more than 1 set of measurements for the same vital sign parameter (ie, SBP, DBP, or HR) on the same date.

Time to event analysis

For time to event analysis/KM plot, time to event (eg, treatment discontinuation, rescue therapy, hypoglycemia, etc) is defined as the number of days from the date of the first administration of double-blind IMP (or the date of randomization if not exposed) to the start date of the first occurrence of the event during the 26-week double-blind treatment period.

Patients who did not experience any event during the 26-week double-blind treatment period are considered censored observations. For time to treatment discontinuation/rescue therapy, censoring date is the date of EOT. For time to severe or documented hypoglycemia, censoring date is date of EOT+1 or date of EOS, whichever is the earliest. Date of EOS will be used if date of EOT is not available. Last contact date will be used if date of EOS is not available.

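### Hypoglycemia is summarised through rescue with no supplementary pre-rescue view, so post-rescue events could dilute, and with a large rescue imbalance hide, an excess on sotagliflozin monotherapy

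*SAP*

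**What the plan says.** - **Window.** SAP 2.4.5.1: "Analyses of hypoglycemia will be performed on the TEAE period as defined in" Section 2.1.4. There the residual treatment epoch runs "up to 10 days (1 day for hypoglycemia) after the last administration of the double-blind IMP". The protocol (observation period of safety endpoints, Section 9.2) ends the on-treatment period 10 days, or 1 day for hypoglycemia, "after the last dose of double-blind IMP, regardless of the introduction of rescue therapy".
- **Rates.** Both incidence rates use the same window as denominator: "here exposure (in days) is the duration of TEAE period, ie, duration of IMP treatment in days +1" (SAP 2.4.5.1).
- **Time to event.** SAP 2.5.4: "For time to severe or documented hypoglycemia, censoring date is date of EOT+1 or date of EOS, whichever is the earliest". Rescue does not censor.
- **Rescue.** Apart from SGLT2 inhibitors, "any approved medication(s) including oral antidiabetic drugs or insulin can be prescribed to treat the hyperglycemia" (Protocol 8.2.1; SAP 2.1.2.1 agrees). The same protocol section keeps the rescued patient on blinded study drug.
- **Attribution.** Protocol 10.4.2 accepts that antidiabetic co-medication "may make it difficult to assess the causal relationship, particularly for hypoglycemia".
- **What is planned around rescue.** SAP 2.4.4.1 repeats the by-visit HbA1c summaries without post-rescue values. SAP 2.4.4.3 gives the number rescued, a KM curve of time to rescue and a patient list. Neither SAP 2.4.5.1 nor Appendix D summarises hypoglycemia before rescue or by rescue status.

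**The concern.** Protocol 4.3.2 says the study is to show efficacy and safety of sotagliflozin as monotherapy. Once a patient starts open-label insulin or another rescue drug, that patient is no longer on monotherapy, yet any later hypoglycemic event counts for the randomised arm on the same footing as an earlier one.

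Rescue follows high fasting glucose. An effective drug should lower fasting glucose, so rescue may well be unequal between arms. If placebo patients are rescued more often and the rescue drugs cause hypoglycemia, the placebo count rises more than the sotagliflozin count and the comparison moves towards no difference.

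Hypoglycemia is a named safety endpoint, and severe hypoglycemia is an event of special interest. Events may be few in patients on diet and exercise, in which case one or two misplaced patients could change the picture. SAP 2.4.5 allows relative risks against placebo to be reported, so a diluted ratio could reach the study report with no pre-rescue figure beside it.

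**Working it through.** The plan states no rescue rate, hypoglycemia rate or mix of rescue drugs, so there is no figure to reproduce. Every rate below is an assumption. Only the arm sizes and glucose thresholds come from the documents.

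**1. Arm sizes (SAP 1.3).** 76 patients randomised 1:1, then about 300 randomised 1:1:1.
- 400 mg versus placebo: 76/2 + 300/3 = 38 + 100 = 138 per arm.
- 200 mg versus placebo: 300/3 = 100 per arm.

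**2. Is more rescue on placebo plausible?** Criterion E17 excludes only a confirmed screening FPG above 270 mg/dL. The rescue threshold falls from 270 to 240 mg/dL after Week 8 and to 200 mg/dL after Week 12 (Protocol 8.2.1). A patient who enters between 200 and 270 mg/dL and does not improve can therefore cross it. Protocol 9.6 reports FPG improvement with sotagliflozin in several studies. More rescue on placebo is a reasonable expectation, but the documents do not state it.

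**3. Added incidence.** Let r be the proportion rescued and h the added risk of an event after rescue, taken as equal in both arms. Shift = (r_placebo − r_sotagliflozin) × h.

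| Rescued, placebo vs sotagliflozin | h | Shift | Patients per 138 |
|---|---|---|---|
| 8% vs 2% | 5% | 0.4 − 0.1 = 0.3 points | 0.4 |
| 12% vs 4% | 10% | 1.2 − 0.4 = 0.8 points | 1.1 |
| 15% vs 5% | 20% | 3.0 − 1.0 = 2.0 points | 2.8 |

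Per 100 patients the same shifts are 0.3, 0.8 and 2.0.

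**4. Effect on a true excess.** Let p be the risk without rescue. Observed risk = 1 − (1 − p)(1 − r·h). Assume 4% on sotagliflozin and 2% on placebo: a difference of 2.0 points and a risk ratio of 2.0.

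| Rescued, placebo vs sotagliflozin | h | Placebo | Sotagliflozin | Difference (points) | Ratio |
|---|---|---|---|---|---|
| any | 0% | 2.00% | 4.00% | 2.0 | 2.00 |
| 5% vs 2% | 10% | 2.49% | 4.19% | 1.7 | 1.68 |
| 10% vs 3% | 10% | 2.98% | 4.29% | 1.3 | 1.44 |
| 20% vs 5% | 10% | 3.96% | 4.48% | 0.5 | 1.13 |
| 20% vs 5% | 20% | 5.92% | 4.96% | −1.0 | 0.84 |

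For example, row three, placebo: 1 − 0.98 × (1 − 0.10 × 0.10) = 1 − 0.98 × 0.99 = 2.98%.

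**5. What complete hiding requires.** Approximately, h must reach the true excess divided by (r_placebo − r_sotagliflozin). For a 2-point excess:
- 5% vs 2%: 0.02/0.03 = 67%
- 10% vs 3%: 0.02/0.07 = 29%
- 12% vs 4%: 0.02/0.08 = 25%
- 20% vs 5%: 0.02/0.15 = 13%
- 30% vs 10%: 0.02/0.20 = 10%

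A 4-point excess cannot be hidden at 5% vs 2%, because 0.04/0.03 exceeds 1.

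**6. If h differs by arm.** Rescued sotagliflozin patients remain on active drug, so h may be higher for them. At 12% vs 4% rescued, with h = 10% on placebo and 30% on sotagliflozin, each arm gains 1.2 points (0.12 × 0.10 = 0.04 × 0.30) and the shift is zero. Beyond a threefold ratio its sign reverses.

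**The case against.** - **Counting through rescue is deliberate and defensible.** It is pre-specified, keeps the randomised groups intact and describes what happens under the treatment policy. This stands, and the present tables should remain the main analysis.
- **Cutting at rescue is informative.** It removes time from the most hyperglycemic patients, possibly unequally by arm. This also stands. A reader might want the monotherapy conclusion to rest on the cut tables alone, but this selection prevents that.
- **Rescue may add little hypoglycemia.** It follows local standard of care, and Protocol 4.1 calls metformin the standard first-line drug in the United States and Europe. Insulin is named as a rescue option; secretagogues are neither named nor excluded. This lowers the plausible h but does not remove the gap.
- **The data will be there to inspect.** Rescue counts, a rescue list and a full hypoglycemia listing are planned, and Protocol 10.4.2 gives the sponsor's safety officer the causality call where the investigator's is unclear. These allow individual events to be traced. They give no pre-rescue rate, denominator or curve, and the planned listing flags event category but not timing relative to rescue.
- **Stronger readings.** A reader might infer that the plan masks any excess, or that the error favours the study drug. Steps 5 and 6 do not support either: full masking needs an extreme combination, and the direction depends on post-rescue risk being similar in the two arms. A reader might also infer that the SAP treats HbA1c differently in principle. It does not: the primary HbA1c analysis keeps post-rescue values, and only a supplementary by-visit presentation drops them.

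**Conclusion.** The gap is real but modest. Hypoglycemia counts, exposure and the KM curve all run through rescue, and no supplementary pre-rescue summary is planned in a monotherapy trial whose own protocol warns about this confounding.

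Post-rescue events can dilute a sotagliflozin excess if three conditions hold: rescue is commoner on placebo, rescue drugs add hypoglycemia risk, and that added risk is not much larger in rescued sotagliflozin patients. Over the assumed ranges in step 3 the shift is 0.3 to 2.0 percentage points, or roughly 0.4 to 2.8 patients per 138. Complete hiding of a 2-point excess needs, for example, 20% versus 5% rescued and about 13% of rescued patients with an event. Because the documents supply none of these rates, neither the size nor the direction of the effect in this trial can be fixed. This is a cheap improvement to the reporting, not an error in the main safety analysis.

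**What to change.** Keep the full TEAE-period tables as the main analysis. In SAP 2.4.5.1 and Appendix D add a supplementary analysis for all arms:

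- n (%) and both rates per 100 patient-years for any, severe and documented symptomatic hypoglycemia, plus the KM presentation, with events and exposure cut at first rescue therapy. Keep the two comparisons as planned: 400 mg against pooled placebo, and 200 mg against Amendment 1 placebo.
- First rescue defined as in SAP 2.1.3, from the reason for treatment on the e-CRF Medication page. Cutting at any new antidiabetic drug would be too broad: Protocol 8.8.1 permits short-term use such as insulin for acute illness, and that should not end a patient's follow-up.
- A flag in the hypoglycemia listing for events after first rescue.
- A sentence saying that the cut at rescue is informative and that the two sets are to be read together.

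**Cost.** One extra set of descriptive tables and less exposure in that set. Rescue records and hypoglycemia onset dates and times are already collected. Since SAP 2.5.3 does not impute medication dates, a short convention for incomplete rescue start dates is also needed. No rescue rule, visit or data collection changes.

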2.4.3.1 Extent of investigational medicinal product exposure

The extent of IMP exposure will be assessed by the duration of IMP exposure.

Duration of IMP exposure is defined as last dose date of double-blind IMP – first dose date of double-blind IMP + 1 day, regardless of unplanned intermittent discontinuations (see [Section 2.5.3](#) for calculation in case of missing or incomplete data).

Duration of IMP exposure will be summarized descriptively as a quantitative variable (number of patients exposed, mean, SD, median, minimum, and maximum). In addition, duration of treatment exposure will also be summarized categorically by numbers and percentages for each of the following categories and cumulatively according to these categories:

- 1 to 28 days,
- 29 to 56 days,
- 57 to 84 days,
- 85 to 126 days,
- 127 to 182 days,
- >182 days.

Additionally, the cumulative duration of treatment exposure will be provided, defined as the sum of the duration of treatment exposure for all patients, and will be expressed in patient years.

Number and percentage of patients by final dose at the end of the treatment will also be presented by each treatment group.

Statistical Analysis Plan

Version: 3

Lexicon Pharmaceuticals Protocol No. EFC14833

Date of Issue: 21-Nov-2019

Covance Study ID: 000000150524

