2.5.3 Missing data

For categorical variables, patients with missing data are not included in calculations of percentages unless otherwise specified. When relevant, the number of patients with missing data is presented.

Derived variables will be considered missing if any of the original variables required to calculate them are missing. For example, if either a baseline assessment or an endpoint assessment is missing for a particular patient, then change from baseline at endpoint will be missing. Depending upon the assessment, analyses may not include all patients in the analysis population, because certain patients in the intended population may have missing data.

Incomplete date of first administration of double-blind IMP

Date/time of first administration is the first non-missing start date/time of double-blind IMP completed in the e-CRF “First dose IMP” module.

For patients who are randomized and dispensed a double-blind treatment kit but who are lost to follow-up just after Visit 3 (eg. only the treatment kit number is reported in the e-CRF “Exposure - treatment period” module without any dose information), the date of first administration will be imputed using the date of randomization. When a patient is randomized but not exposed, “Not taken” should be ticked in the e-CRF “First dose IMP” module.

Handling of computation of treatment duration if IMP end of treatment date is missing

For the calculation of the treatment duration, the date of the last dose of double-blind IMP is equal to the date of last administration reported on the e-CRF “Treatment status library” page. If this date is missing, the exposure duration should be left as missing.

The last dose administration should be clearly identified in the case report form and should not be approximated by the last returned package date.

Handling of medication missing/partial dates

No imputation of medication start/end dates or times will be performed. If a medication date or time is missing or partially missing and it cannot be determined whether it was taken prior or concomitantly, it will be considered a prior, concomitant, and post-treatment medication.

Handling of adverse events/hypoglycemia with missing or partial date/time of onset

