Missing or partial adverse event/hypoglycemia onset dates and times will be imputed so that if the partial adverse event/hypoglycemia onset date/time information does not indicate that the adverse event/hypoglycemia started prior to treatment or after the treatment-emergent adverse event period, the adverse event/hypoglycemia will be classified as treatment-emergent. No imputation of adverse event end dates/times will be performed. These data imputations are for categorization purpose only and will not be used in listings. No imputation is planned for date/time of adverse event resolution.

Statistical Analysis Plan

Version: 3

Lexicon Pharmaceuticals Protocol No. EFC14833

Date of Issue: 21-Nov-2019

Covance Study ID: 000000150524

Handling of adverse events/hypoglycemia when date and time of first IMP administration is missing

When the date and time of the first double-blind IMP administration is missing, the day of randomization should be considered as the start date of TEAE period (see [Section 2.1.4](#)). The exposure duration should be kept as missing.

Handling of adverse events/hypoglycemia when IMP end of treatment date is missing

For the purpose of defining TEAE period, the date of the last administration of double-blind IMP is equal to the date of the last administration reported on the e-CRF “Treatment Status Library” page.

If the date of last administration reported on the e-CRF “Treatment Status Library” page is

- Partially missing, it will be imputed with a date as late as possible before or on the date of last available information on eCRF “Completion of End of Study/Follow-up”.
- Completely missing, it will be imputed with the date of last available information on eCRF “Completion of End of Study/Follow-up” page.

If the date of last available information on eCRF “Completion of End of Study/Follow-up” page is

- Partially missing, it will be imputed with a date as late as possible.
- Completely missing, all adverse events occurred on or after the first administration of double-blind IMP will be considered as treatment emergent adverse events.

Handling of missing assessment of relationship of adverse events to IMP

If the assessment of the relationship to IMP is missing, the relationship to IMP has to be assumed and the adverse event considered as such in the frequency tables of possibly related adverse events, but no imputation should be done at the data level.

Handling of missing severity/grades of adverse events

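### The patient-level hypoglycemia incidence rate counts person-time after the first event, and the SAP does not settle which exposure feeds either rate when a dosing date is missing

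*SAP*

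**What the plan says.** Protocol 11.4.3.2 asks for two hypoglycemia rates, one counting patients and one counting events, and does not define the person-time. SAP 2.4.5.1 calls both incidence rates and supplies the formulas:

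- Patient-level rate: "calculated as the number of patients with at least 1 event / total exposure in 100 patient-years".
- Event rate: "calculated as the total number of events / total exposure in 100 patient-years".
- Exposure for both: "here exposure (in days) is the duration of TEAE period, ie, duration of IMP treatment in days +1".

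SAP 2.4.3.1 defines treatment duration as "last dose date of double-blind IMP – first dose date of double-blind IMP + 1 day" and refers missing dates to 2.5.3. SAP 2.1.4 ends the TEAE period "up to 10 days (1 day for hypoglycemia) after the last administration of the double-blind IMP".

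SAP 2.5.3 has separate rules for exposure and for event classification:

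- Last-dose date missing, computing exposure: "If this date is missing, the exposure duration should be left as missing".
- Last-dose date missing, defining the TEAE period: "Completely missing, it will be imputed with the date of last available information on eCRF" (the end-of-study page). A partial date is set as late as possible.
- First-dose date missing, in a rule covering adverse events and hypoglycemia: the TEAE period starts on the day of randomization, and exposure duration stays missing.

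For the Kaplan-Meier curves, SAP 2.5.4 says that "time to event (eg, treatment discontinuation, rescue therapy, hypoglycemia, etc) is defined as the number of days" from first dose to first occurrence. Censoring falls back to the end-of-study date, then to the last contact date, when the end-of-treatment date is unavailable. SAP 2.4.5.1 plans such a curve for severe or documented symptomatic hypoglycemia, not for any hypoglycemia.

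**The concern.** There are two separate issues.

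First, the patient-level numerator counts a patient once. After the first event that patient cannot add to it, yet the remaining time on treatment still enters the denominator. A figure labelled an incidence rate would normally be read as first events per unit of time at risk. The planned figure is lower than that, and the gap widens as the proportion with an event rises, so it differs between arms if hypoglycemia does.

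Second, the two descriptions of exposure in 2.4.5.1 agree only when both dosing dates are known. When one is missing, the patient's events still count as treatment-emergent, but whether the patient brings any person-time depends on which description the programmer follows. Two programmers could produce different rates from the same data.

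At stake is the accuracy and reproducibility of the reported rates for a named safety endpoint (Protocol 9.2).

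**Working it through.** The documents give no expected hypoglycemia rate, event proportion or count of missing dates, so there is no planned figure to reproduce. The event proportions and missing-date counts below are assumptions shown as a range.

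**Time after the first event (patient-level rate only)**

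Inputs: 182 days of treatment (26 weeks) plus the 1-day hypoglycemia window gives T = 183 days. Assume everyone is followed for T, the hazard of a first event is constant, and a proportion p has at least one event.

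- Planned rate = Np / (N × T) = p / T
- Rate with time stopped at the first event = −ln(1 − p) / T
- Planned ÷ at-risk = p / (−ln(1 − p)), whatever N is

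Example, N = 100 and p = 10%. Full exposure is 100 × 183 / 365.25 = 50.10 patient-years. The planned rate is 10 / 50.10 × 100 = 19.96 per 100 patient-years. The at-risk rate is 0.10536 / 183 × 365.25 × 100 = 21.03.

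| p (assumed) | Planned, per 100 PY | At-risk, per 100 PY | Ratio | Shortfall |
|---|---|---|---|---|
| 1% | 2.00 | 2.01 | 0.995 | 0.5% |
| 2% | 3.99 | 4.03 | 0.990 | 1.0% |
| 5% | 9.98 | 10.24 | 0.975 | 2.5% |
| 10% | 19.96 | 21.03 | 0.949 | 5.1% |
| 20% | 39.92 | 44.54 | 0.896 | 10.4% |

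The event rate has no such shortfall: a patient can have further events, so all exposure belongs in its denominator.

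**Missing dosing dates (both rates)**

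With complete dates the two descriptions agree: last dose − first dose + 1, plus one residual day. With a missing date they part:

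| | TEAE-period reading | Treatment-duration reading |
|---|---|---|
| Events | Kept | Kept |
| Last-dose date missing | End date imputed, time kept | Duration missing, time lost |
| First-dose date missing | Start set to randomization, time kept | Duration missing, time lost |

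If m of N patients lose their time and each would have contributed d days, with everyone else contributing 183 and missing durations simply dropping out of the sum, both rates are inflated by

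[(N − m) × 183 + m × d] / [(N − m) × 183].

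The maximum, at d = 183, is N / (N − m):

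- 1 of 100: 100 / 99 = 1.010, or +1.0%
- 5 of 100: 100 / 95 = 1.053, or +5.3%
- 5 of 138 (38 + 100, the approximate size of the 400 mg and pooled placebo groups): 138 / 133 = 1.038, or +3.8%

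For patients lost early it is less: 5 of 100 with d = 29 gives 1 + (5 × 29) / (95 × 183) = 1.008, or +0.8%. Under the TEAE-period reading the inflation is zero.

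**The case against.** The formula is printed in full, so nobody is misled about the denominator, and it implements what Protocol 11.4.3.2 asks for. Patients with events over total exposure is a recognizable exposure-adjusted summary, and the Kaplan-Meier curve already gives a time-to-first-event view. This supports relabelling as an acceptable minimum. It does not make the quantity an incidence rate, and no curve is planned for any hypoglycemia, the broadest category.

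The effect may also be very small. Patients are on diet and exercise only, and other antidiabetic agents are barred before rescue apart from short-term use. At 1 to 2% of patients with an event the shortfall is 1% or less. That stands: nothing in the documents shows that the upper rows of the table apply.

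A reader might infer that treatment comparisons are biased toward no difference. Dividing two printed rates would indeed give 2.00 rather than 2.12 for an assumed 10% against 20%. But no hypoglycemia rate ratio is planned. SAP 2.4.5 describes safety analysis as essentially descriptive and mentions only optional relative risks, and a relative risk computed from proportions does not use person-time.

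On missing dates, the exposure sentence names the TEAE period first, and SAP 2.5.3 imputes dates for exactly that period. On that reading nothing is lost. This is a fair reading, but the same sentence then restates exposure as treatment duration, which 2.5.3 leaves missing, and the SAP does not say which prevails.

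Finally, the imputed end date is a deliberately late choice made to classify events. Used as a denominator it may credit days off drug and lower the rate. That is a real, small cost of the remedy.

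**Conclusion.** Both issues stand, at modest size.

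- The patient-level rate, and only that rate, understates the incidence of first events by about 0.5% at p = 1%, 2.5% at 5%, 5% at 10% and 10% at 20%. This rests on a constant hazard, full follow-up and assumed proportions. The understatement is larger in an arm with more hypoglycemia.
- The exposure definition conflicts with itself when a first- or last-dose date is missing. Under one reading both rates are inflated, by at most about 1% for 1 of 100 patients and 5% for 5 of 100 (assumed counts); under the other there is no effect. A reader might conclude that the SAP definitely discards this person-time. The text does not settle that, so the finding is an unresolved conflict that needs one clarifying sentence.

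It would also be wrong to conclude that both rates use the wrong person-time in general: with complete dates the events-per-exposure rate is correct. Nothing here touches alpha, power, sample size or any efficacy conclusion.

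**What to change.** Amend SAP 2.4.5.1 in two places.

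1. Patient-level rate: for each category, sum the time from the start of the TEAE period to the first event of that category, or to the end of the period if there is none. First-event times are already specified for the severe or documented symptomatic curve; any hypoglycemia needs its own first-event date. At minimum, drop the incidence-rate label and call the figure patients with events per total exposure. Leave the event-rate formula as it is.
2. Both rates: state that exposure runs between the same TEAE start and end dates, imputed under SAP 2.5.3 where needed, that classify the events, and remove the equation with treatment duration or limit it to patients with complete dates. Where the end-of-study date is also completely missing, 2.5.3 keeps the events but sets no end date; the last-contact fallback already used for the Kaplan-Meier curves in 2.5.4 would close that gap.

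Because imputed end dates may add some off-drug days, report by arm how many patients had an imputed start or end date.

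The cost is a few lines of text and minor programming. No new data are needed, and the protocol wording need not change.
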